## STATEMENT OF COMPLIANCE

[The trial will be carried out in accordance with International Council on Harmonisation Good Clinical Practice (ICH GCP) and the following:

- United States (US) Code of Federal Regulations (CFR) applicable to clinical studies (45 CFR Part 46, 21 CFR Part 50, 21 CFR Part 56, 21 CFR Part 312, and/or 21 CFR Part 812).

National Institutes of Health (NIH)-funded investigators and clinical trial site staff who are responsible for the conduct, management, or oversight of NIH-funded clinical trials have completed Human Subjects Protection and ICH GCP Training.

The protocol, informed consent form(s), recruitment materials, and all participant materials will be submitted to the IRB for review and approval. Approval of both the protocol and the consent form(s) must be obtained before any participant is consented. Any amendment to the protocol will require review and approval by the IRB before the changes are implemented to the study. All changes to the consent form(s) will be IRB approved; a determination will be made regarding whether a new consent needs to be obtained from participants who provided consent, using a previously approved consent form.]

## 1 PROTOCOL SUMMARY

*No text is to be entered in this section; rather it should be included under the relevant subheadings below. It may be useful to complete this section after the relevant sections in the protocol have been completed.*

### 1.1 SYNOPSIS

**Title:** Feasibility of conducting an online family dyadic/couple skills training for Black adults enrolled in a behavioral weight loss intervention

**Grant Number:**

TEAM Plus is an in-person 3-month family enhanced BWL intervention

**Study Description:**

designed for Black adults consisting of a family dyadic skills training and core behavioral weight loss sessions testing the feasibility and acceptability of an interactive counselor-led online training, the family dyadic skills training will be delivered online using a web-conferencing platform (e.g., Zoom).

**Objectives\* :**

**Primary Aim:** To test the feasibility of implementing and acceptability of an online family dyadic/couple skills

**Secondary Aim:** To explore the experience of administering a family dyadic/couple skills training online from a counselor perspective (i.e., facilitators, barriers, acceptability).

**Endpoints\* :**

Described previously

**Study Population:**

Participants must be 1) ≥18 years of age, 2) self-identify as Black/African American, 3) reside in the Raleigh/Durham/Chapel Hill area. (n=19)  
Pilot

**Phase\* or Stage:**  
**Description of Sites/Facilities Enrolling Participants:**

Participants will be recruited from community organizations, local universities, through social media and word of mouth.

**Description of Study Intervention/Experimental Manipulation:**

The study intervention is a 3-month behavioral weight loss intervention adapted from the Diabetes Prevention Program (DPP). Core group sessions, and individual or small group family skills trainings are included. Family skills trainings are delivered in person or virtually.

[figure not shown]
**Study Duration\* :**

7 months

**Participant Duration:**

4 months

### 1.2 SCHEMA

### 1.3 SCHEDULE OF ACTIVITIES

	Pre-screening (Pre-consent)	Consent/ Baseline (Pre- Visit 1)	Visit 1 Day 1 ±7	Visit 2 Day 7 ±7	Visit 3 Day 14 ±7	Visit 4 Day 21 ±7	Visit 5 Day 35 ±7	Visit 6 Day 49 ±7	Visit 7 Day 79 ±7	Post Assessment Day 91 ±7
Review Eligibility	X									
Informed Consent		X								
Demographics		X								
Clinical history		X								
Height		X								X
Outcome Evaluation										
Weight	X	X	X	X	X	X	X	X	X	X
Surveys	X									X
Randomization		X								
Control & Experimental Interventions		X	X	X	X	X	X	X	X	
Adverse Events Reporting	X				X	X	X	X	X	X

## 2 INTRODUCTION

### 2.1 STUDY RATIONALE

See section 2.2

### 2.2 BACKGROUND

Nearly half (49.9%) of Black adults in the United States live with obesity. Black adults are underrepresented in standard behavioral weight loss interventions (BWLI) and experience sub-optimal weight loss outcomes when included in such programs. Cultural adaptations to BWLI that recognize the family behavioral context and address the cultural value of family among Black populations are needed to improve weight loss outcomes. Prior research, including our randomized controlled pilot, Together, Eating and Activity, Matter (TEAM), have incorporated family skills training to enhance family involvement, targeting cohesion and communication, in addition to core weight loss curriculum. However, family inclusion in weight loss interventions can result in additional barriers to retention and adherence.

Technology has become an attractive delivery format to increase reach to at-risk populations, as a well-designed online program can address issues of timely access and geographical location (or distance from program sites), which are linked to low retention of Black participants. However, technology uptake among Blacks populations still lags due to mistrust, skepticism, concerns about confidentiality, privacy, and remote interaction with staff. Increases in acceptance and utilization of telemedicine and mobile-health were reported during the COVID-19 pandemic. Considering the time and location burden already associated with behavioral weight loss sessions, it is important to identify strategies to increase access that are both feasible and acceptable in the target population. Currently the feasibility and acceptability of an online family dyadic skills training is unknown among Black adults.

### 2.3 RISK/BENEFIT ASSESSMENT

#### 2.3.1 KNOWN POTENTIAL RISKS

The possible risks and discomforts from being in this study are few and are listed below.

- We do not think there is risk from the dietary advice given as part of the study
- Those who increase their level of physical activity may experience minor muscle pain, but this type of activity rarely causes serious health problems such as chest pain or asthma.
- In all studies, there is a very slight chance of loss of privacy (that is, others may see your study information). As stated below, we will do all we can to make sure this does not happen.

### 2.3.2 KNOWN POTENTIAL BENEFITS

Research is designed to benefit society by gaining new knowledge. A benefit from being in this study is improvement in lifestyle and losing weight. However, some not benefit from being in this study

### 2.3.3 ASSESSMENT OF POTENTIAL RISKS AND BENEFITS

The potential risks are small, as noted above. We outline our approach to minimizing risk above. We believe there is much to be gained from this study, especially in the context of minimal risk.

## 3 OBJECTIVES AND ENDPOINTS

OBJECTIVES	ENDPOINTS	JUSTIFICATION FOR ENDPOINTS	PUTATIVE MECHANISMS OF ACTION
Primary			
Primary Aim: To test the feasibility of implementing and acceptability of an online family dyadic/couple skills	Feasibility will be measured by the number of participants who consent, and the percent of dyads that attend both sessions.  Acceptability will be measured by a satisfaction survey complete by both dyad members	Primary Outcome	
Secondary			
Secondary Aim: To explore the experience of administering a family dyadic/couple skills training online from a counselor perspective (i.e., facilitators, barriers, acceptability).			

## 4 STUDY DESIGN

### 4.1 OVERALL DESIGN

Randomized controlled pilot enrolling 20 participants in a weight loss program and followed for 3 months. Participants will be randomized 1:1

- Arm 1: Family Skills Training In-person;
- Arm 2: Family Skills Training On-line

Randomized assignment will be completed by a random number generator in Excel.

From the perspective of NIH, this is a single site study as the intervention is given by one investigational team.

The acronym for the study is TEAM Plus (Together Eating & Activity, Matter). The names of the study arms are given above.

## 4.2 SCIENTIFIC RATIONALE FOR STUDY DESIGN

*Describe the rationale for the type and selection of control or comparison condition(s) and study design. Discuss known or potential problems associated with the control group chosen in light of the specific disease, health behavior, and intervention(s) being studied.*

<Insert text>

## 4.3 JUSTIFICATION FOR INTERVENTION

Technology offers a promising way to reach at-risk groups, like Black communities, by reducing barriers such as distance and scheduling that often lead to low participation in weight loss programs. However, Black populations have been slower to adopt technology due to concerns about trust, privacy, and remote communication. During the COVID-19 pandemic, more people began using telemedicine and mobile health tools, showing potential for wider acceptance. Given the time and travel demands of traditional weight loss programs, it is important to find tech-based solutions that are both practical and trusted by the target population.

## 4.4 END-OF-STUDY DEFINITION

The end of study is defined as completing the 3 month follow-up visit.

# 5 STUDY POPULATION

## 5.1 INCLUSION CRITERIA

Participants must

- 1) be ≥18 years of age,

- 2) self-identify as Black/African American,
- 3) reside in the Raleigh/Durham/Chapel Hill area,
- 4) a family member willing to participate in program sessions together, and
- 5) have internet access.

## 5.2 EXCLUSION CRITERIA

An individual who does not meet all of the above criteria on section 5.1 will be excluded from participation in this study.

A participant cannot be taking any weight loss medication.

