#### 7.2 PARTICIPANT DISCONTINUATION/WITHDRAWAL FROM THE STUDY

Participants are free to withdraw from participation in the study at any time upon request.

Participants will be withdrawn according to protocol for the following reasons:

- Other medical diagnosis typically associated with significant weight loss (5% or more of body weight). In addition to malignancy, examples include nonmalignant gastrointestinal disease, endocrinopathies, infectious disease, rheumatologic diseases, etc. As [name] (study Co-I, general internist) will be blinded to participants' study group assignment, he will adjudicate in these situations, seeking consultation from medical colleagues as appropriate.
- New diagnosis of medical condition such that participation in a behavioral weight loss intervention is no longer appropriate.
- Permanent change in living situation (e.g. from home to nursing home) such that the participant has limited food options.

Pregnancy: Study participants who become pregnant may continue to participate in the study with the understanding that weight loss goals will be suspended during pregnancy through 3 months postpartum. If a pregnant participant wishes to continue with counseling session during pregnancy, the focus on counseling will be on dietary quality. The participant may resume full participation 3 months postpartum. Any data collected while the participant is pregnant will be censored and follow-up data will not be collected until the participant is 6 months postpartum.

A participant will be considered lost to follow-up if we are unable to contact him/her according to this algorithm.

- Attempts at telephone contact:
  - We will call up to 5 times over a 2 week period. We will attempt 2 calls during regular work hours (8:30 to 5:30 on weekdays) and 3 after hours, including Mon-Thurs evening between 5:31 and 9:00 pm and on Saturday calling between 8:30 and 5:30 pm.
  - We will leave up to 2 phone messages.
  - If no contact is made over this initial 2 week period as outlined above, we will undertake more limited contact attempts for an additional 2 weeks including up to 2 phone calls per week, 1 during business and the other during evening hours or on the weekend.
- Email: If a participant gives us permission to contact by email, we will send up to 4 weekly emails.
- Text: If a participant gives us permission to contact by text, we will send up to 4 weekly texts.

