### 8.3.9 REPORTING OF PREGNANCY

Study participants who become pregnant may not continue to participate in the study due to the study duration (3 months) and the anticipated duration of a full term pregnancy

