#### 10.1.1.2 CONSENT PROCEDURES AND DOCUMENTATION

Contacting participants who expressed interest to assess eligibility

- During eligible calls, data are entered into the eligibility questionnaire.
- If a potential participant is interested and eligible, staff will email the consent forms to this individual and an appointment will be made for the consent phone call in about 1 week.

Consent phone call

- At this phone call, key components of the consent form are reviewed in detail to insure that the potential participant understands what participation entails. If the potential participant agrees to sign consent form via e-consent, instructions are given on how to do so. If the potential participant prefers to sign at the enrollment visit, then verbal consent to complete baseline questionnaires before the enrollment visit will be obtained, as approved by the IRB.
- Instructions for completing baseline forms, on-line, are given and plans to complete these forms are made accordingly. An appointment date is set for the baseline visit.

**Enrollment visit and randomization:** At the enrollment visit, all questions will be answered about the study and those who did not sign the consent forms on-line will sign the consent form. Upon completion of baseline measures the participant will be ready for randomization. The research assistant will use a secure excel document to ascertain randomization assignment

---

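### Sections 7.2 and 8.3.9 give opposite rules for a participant who becomes pregnant, the 7.2 rule cannot be met within the study, and the written entry criteria do not mention pregnancy

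*Combined protocol and SAP*

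**What the plan says.** **Pregnancy during the study.** Section 7.2 states: "Study participants who become pregnant may continue to participate in the study". Weight loss goals are suspended until 3 months postpartum, when full participation may resume. Data collected during pregnancy are censored, and "follow-up data will not be collected until the participant is 6 months postpartum". Section 8.3.9 states the reverse: "Study participants who become pregnant may not continue to participate in the study due to the study duration (3 months", and also gives the length of a full-term pregnancy as a reason.

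**Study length.** The synopsis (1.1) gives a participant duration of 4 months and a study duration of 7 months. Section 4.4 adds: "The end of study is defined as completing the 3 month follow-up visit". The schedule (1.3) puts the post assessment at day 91 ± 7.

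**Entry.** Section 5.1 lists age, race, residence, a willing family member and internet access. Section 5.2 excludes anyone who fails one of these, and adds "A participant cannot be taking any weight loss medication". Neither section mentions pregnancy. In 1.3, "Review Eligibility" is marked only at pre-screening and clinical history only at consent/baseline. Section 10.1.1.2 describes the screening call ("During eligible calls, data are entered into the eligibility questionnaire") and then moves from completed baseline measures to randomisation.

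**Stopping.** Section 7.1 makes no attempt at follow-up for a participant who withdraws or is withdrawn. It invites follow-up from one who leaves only the intervention and is willing to be measured. Section 7.2 plans no replacement.

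**The concern.** Both pregnancy paragraphs are current text about the same event, and neither refers to the other. The choice changes the data. Under 7.2, everything collected during the pregnancy is censored and follow-up is put off to a date after the study has closed. Under 8.3.9, read together with the withdrawal rule in 7.1, she leaves and her 3-month satisfaction survey is not sought. That survey is the acceptability half of the primary aim. With 20 participants planned and no replacement, each participant handled one way or the other is 1/20 = 5% of the sample.

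The entry criteria leave a related gap. A person already pregnant passes everything in 5.1 and 5.2 and could be randomised to a weight loss programme. Neither pregnancy paragraph is written for her, since both speak of participants who become pregnant.

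**Working it through.** The plan gives no figure to reproduce on this point. The check compares the two rules and then does calendar arithmetic on 7.2.

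**1. The two rules.**

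| | 7.2 | 8.3.9 |
|---|---|---|
| Event | becomes pregnant | becomes pregnant |
| Participation | may continue | may not continue |
| Weight loss goals | suspended to 3 months postpartum | not addressed |
| Follow-up | not before 6 months postpartum | not addressed |
| Reason given | none | study duration and length of pregnancy |

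The participation rows cannot both be followed.

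**2. Inputs for the timing.** Participant duration 4 months and study duration 7 months (1.1). End of study at the 3-month visit (4.4). Post-assessment window closes at day 91 + 7 = 98 (1.3). Follow-up wait 6 months and resumption wait 3 months after delivery (7.2). Length of pregnancy 6 to 9 months: an assumption, not in the documents. Conception is taken to occur between her start and month 3.

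**3. The wait alone.** Ignoring the pregnancy itself, 6 − 4 = 2 months. The postpartum wait is already longer than the whole of participation.

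**4. Earliest follow-up**, in months after her start = month of conception + length of pregnancy + 6.
- Conception at the start: 0 + (6 to 9) + 6 = 12 to 15.
- Conception at month 3: 3 + (6 to 9) + 6 = 15 to 18.
- Overall: 12 to 18 months, against 4 for participation and 7 for the study. Even someone who starts on the study's first day is overdue by 12 − 7 = 5 months at the least.

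**5. Earliest resumption of full participation** = month of conception + length of pregnancy + 3.
- Conception at the start: 0 + (6 to 9) + 3 = 9 to 12.
- Conception at month 3: 3 + (6 to 9) + 3 = 12 to 15.
- Overall: 9 to 15 months, also after the study has closed.

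**6. Entry.** Going through the five criteria in 5.1 and the medication exclusion in 5.2, being pregnant fails none of them. No step in 1.3 or 10.1.1.2 turns a pregnancy disclosed in the baseline history into a reason not to randomise. Section 5.4 already has the category such a step would use: someone who consents but is not assigned to the intervention.

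**The case against.** The contradiction itself is hard to defend. The best case on the other side concerns how much to build on it, and several parts of that case stand.

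- **Unsuitable medical conditions in general.** A reader might infer that the entry rules ignore every condition that 7.2 later treats as a reason to stop, such as "New diagnosis of medical condition such that participation in a behavioral weight loss intervention is no longer appropriate". The documents do not support that. The first withdrawal bullet in 7.2, on diagnoses associated with significant weight loss, is not limited to new diagnoses and is adjudicated by the internist co-investigator. Section 5.4 gives weight loss above 10% before visit 1 as a screen-failure example. Section 8.3.4 treats conditions present at screening as baseline and records deterioration as an adverse event. What remains is a small mismatch in wording.
- **The missing check after clinical history.** This may look like a defect in its own right. But every criterion now listed can be settled by phone, and medication use is reassessed at each study visit (6.5). A later check matters mainly once pregnancy is made a criterion.
- **Pregnancy as a safety signal.** One might read 8.3.9 as the sponsor judging the programme unsafe in pregnancy. The reasons it states are about duration. Section 7.2 would still offer counselling on dietary quality, and the study is described as minimal risk.
- **A gap of about 84 days.** For a woman delivering on day 1, 6 months is 6 × 365/12 = 182.5 days, and 182.5 − 98 = 84.5 days after the window closes. She was pregnant before entry, so the 7.2 rule for those who become pregnant does not cover her, and the figure should not be used.
- **Unseen screening.** The eligibility questionnaire is not reproduced and the consent pages were removed. Section 5.5 refers to a BMI criterion that 5.1 does not list, so the list in 5.1 and 5.2 may not be the whole screen. One cannot conclude that pregnant people would in fact be enrolled.
- **Effect on the endpoints.** None of the primary measures (consent count, dyad attendance, satisfaction) is a weight outcome. Simply adopting 8.3.9 could lose the survey through 7.1. This objection is right, and the fix has to allow for it.

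**Conclusion.** The point holds for pregnancy. Sections 7.2 and 8.3.9 are opposite instructions for one event. The 7.2 version cannot be carried out: its 6-month wait is 2 months longer than participation, whatever the length of pregnancy. With the assumed 6 to 9 months, follow-up lands 12 to 18 months after the start of a study planned to last 7. The written entry criteria also admit someone already pregnant, subject to screening that the documents do not show.

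Severity is minor. The documents give no pregnancy rate, so the number affected is unknown and may be zero among 20 participants. The case rests on inconsistent, unworkable wording, not on demonstrated harm or on bias in the primary outcome. The wider reading, that the plan has no protection against unsuitable medical conditions, is not supported.

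**What to change.** 1. **One pregnancy rule.** Replace the 7.2 paragraph with a rule consistent with 8.3.9: a participant who becomes pregnant stops the weight loss intervention. State that she is handled as stopping the intervention only, so that the follow-up route in 7.1 applies. She is then invited to complete the 3-month satisfaction survey, and weight data taken during pregnancy are censored. Section 7.1 currently offers this route to those who ask to stop, so the new rule should extend it explicitly. Section 8.3.9 should then speak of the intervention and not of the study.

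2. **Entry.** Add current pregnancy to 5.2. Ask at the eligibility call and confirm with the baseline clinical history before randomisation, with one added mark in 1.3 and one sentence in 10.1.1.2. Anyone found pregnant at that stage is a screen failure under 5.4. Say whether the exclusion also applies to the family member, and what happens to the remaining dyad partner if one member stops.

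3. **Optional.** Repeat the 7.2 medical-inappropriateness reason at entry. Since 7.2 and 5.4 already cover part of this, it is a consistency edit only.

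**Cost.** Wording in 5.2, 7.1, 7.2, 8.3.9 and 10.1.1.2, one schedule mark, and one question if the questionnaire or history does not already ask it. There may be a few more screen failures; the number cannot be estimated from the documents. The change does not recover postpartum follow-up, which could not have been collected within the study anyway, but it keeps the survey.

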## 5.3 LIFESTYLE CONSIDERATIONS

During this study, participants are asked to:

- Follow the lifestyle recommendations for both dietary change and to be modestly physically active.
- If they are unable to make the recommended changes, they will continue in the study. Specifically, participants will not be excluded if they fail to achieve lifestyle goals.

## 5.4 SCREEN FAILURES

Screen failures are defined as participants who consent to participate in this study but are not subsequently assigned to the study intervention or entered in the study. Individuals who do not meet the criteria for participation in this trial (screen failure) because of meeting one or more exclusion criteria that are likely to change over time may be rescreened. Examples include weight loss of more than 10% of their baseline weight prior to the visit 1 or moving away from the Raleigh/Durham/Chapel Hill area.

